# Statistical Analysis Plan

## 1.0 SYNOPSIS OF STUDY DESIGN

### 1.1 Purpose of the Statistical Analysis Plan

This statistical analysis plan (SAP) is intended to provide a detailed and comprehensive description of the planned methodology and analysis to be used for clinical investigation plan (CIP) [REDACTED] the LBBAP Data Collection Registry. This plan is based on the Version B of the Clinical Investigation Plan.

### 1.2 Clinical Investigation Objectives

The objective of this retrospective chart review study is to evaluate the safety and effectiveness of left bundle branch area (LBBA) pacing/sensing in patients already implanted with the Tendril STS 2088 lead.

### 1.3 Clinical Investigation Design

This is a retrospective, observational, non-controlled, chart review study designed to evaluate the safety and effectiveness of LBBA pacing/sensing in patients already implanted with the Tendril STS 2088 lead.

Data on a minimum of 220 attempted subjects will be included in order to have 190 evaluable subjects in this registry. The chart review will be conducted at up to 20 centers worldwide. The chart review will be conducted at up to 20 participating centers worldwide.

The clinical investigation is a retrospective chart review and therefore involves no pain, discomfort, fear, and any other foreseeable risk as possible for subjects.

### 1.4 Endpoints

#### 1.4.1 Primary Safety Endpoint

The primary safety endpoint evaluates freedom from left bundle branch area pacing (LBBAP) lead related serious adverse device effects (SADEs) through 6 months post-implant attempt.

The primary safety endpoint evaluates a LBBAP lead related SADE rate which is an appropriate measure for safety and consistent with the primary safety endpoints used for evaluating performance of the transvenous right ventricular lead. It is appropriate to evaluate the safety through 6 months since it is known that a great majority of complications occur through 3 - 6 months after the implantation.

#### 1.4.2 Primary Effectiveness Endpoint

The primary effectiveness endpoint evaluates the composite success rate of acceptable capture thresholds and sense amplitudes for LBBAP through 6 months post-implant. This analysis will be performed with only patients who are successfully implanted with the Tendril™ STS 2088 lead in the LBBA (see details in CIP section 6.1.2). Acceptable ranges for sensing and pacing are shown below:

Parameter	Acceptable values
Pacing voltage	Pacing threshold $\leq$ 2.0V
Sense amplitude	LBBA sense amplitude $\geq$ 5.0 mV or $\geq$ value at implant

## Statistical Analysis Plan

The primary effectiveness endpoint evaluates the ability to pace and sense when the Tendril™ STS 2088 lead is implanted in the LBBA. The evaluation of a composite success rate of acceptable pacing thresholds and sensing amplitudes is similar to the primary effectiveness endpoints used in for a prior transvenous pacing lead (Tendril FSR 1699T). The 6-month timepoint for assessing the primary effectiveness endpoint is an appropriate time period since these electrical measurements have been demonstrated to be stable starting as early as 1 month post-implant.

### 1.4.3 Descriptive Data and Endpoints

Descriptive data and endpoints are reported using only summary statistics and no hypothesis tests will be performed.

- Demographics (if provided): sex at birth, age range
- Indication for pacemaker or CRT-P/D implant
- Cardiovascular (CV) history and other significant medical conditions
- Procedure and device-related adverse events
- Implant success rate for LBBAP lead and reasons for unsuccessful implant
- Number of repositioning attempts at implant
- Overall procedure time: skin-to-skin
- Implant procedure time: vascular access to lead fixation
- Fluoroscopy time and radiation dose
- Implant tools used (i.e., catheter, stylet, etc.): manufacturer, model#
- Capture threshold, pulse width, sense amplitude, and pacing impedance at all follow-up visits
- Mortality
- QRS duration and morphology (if available)
- NYHA classification (if available)
- LVEF, LVEDV, LVESV (if available)

## 2.0 ANALYSIS CONSIDERATIONS

### 2.1 Analysis Populations

#### 2.1.1 Enrolled Population

This analysis population will include enrolled subjects who have been attempted to implant for the Tendril™ STS 2088 lead in the LBBA.

#### 2.1.2 Successfully Implanted Population

The successfully implanted population includes enrolled subjects who are successfully implanted with the Tendril STS 2088 lead in the left bundle branch area (refer to CIP Section 6.1.2).

### 2.2 Statistical Methods

#### 2.2.1 Descriptive Statistics for Continuous Variables

For continuous variables (e.g., age), results will be summarized with the numbers of observations, means, and standard deviations, with quartiles, minimums, maximums, and 95% confidence intervals for the means as per the table mockups.

## Statistical Analysis Plan

### 2.2.2 Descriptive Statistics for Categorical Variables

For categorical variables (e.g. gender, race, etc.), results will be summarized with subject counts and percentages/rates, and where specified in the table mockups, with exact 95% Clopper-Pearson confidence intervals.

### 2.2.3 Survival Analyses

Survival analysis will be conducted to analyze time-to-event variables. Subjects without events will be censored at their last known event-free time point. Survival curves will be constructed using Kaplan-Meier estimates.

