#### 5.2 Subject Screening and Informed Consent

##### 5.2.1 Subject Recruitment and Screening

Research personnel at each participating center will identify consecutive subjects with an attempt of the Tendril™ STS 2088 lead implant in the LBBA, which comprise the “primary registry” cohort. Subjects are excluded if there is not 6 months ( $\pm$  3 months) of follow-up data available in the medical records after the LBBAP implant attempt.

A member of the site’s clinical investigation team previously trained to the CIP must evaluate patients for the general clinical investigation eligibility criteria, and if applicable, will enter the patients into a site-specific recruitment/screening log. A patient who does not satisfy all general eligibility criteria prior to informed consent (if required) is considered a recruitment failure and should not be enrolled in the clinical investigation.

In case the subject does not meet all inclusion criteria or meets any of the exclusion criteria, the subject is considered a screening failure. The Principal Investigator or the delegated clinical investigation personnel will record the screening failure in the hospital records and on a recruitment/screening log as required.

Each participating site can enroll up to 25 subjects. The sponsor's approval must be obtained to enroll more than 25 subjects in the registry.

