### 5.3.2 Inclusion Criteria

#### 5.3.2.1 Inclusion Criteria

- 1) Subject has a de novo attempted implant of the Tendril™ STS 2088 lead in the Left Bundle Branch Area on or before January 31, 2023 and subject's medical records contain data through at least 6 months (+/- 3 months) after LBBAP implant attempt
- 2) Subject is  $\geq$  18 years of age or the legal age, whichever age is greater
- 3) For sites where the governing IRB/EC has not granted a waiver of informed consent, subject has either been informed of the nature of the clinical investigation using a privacy notice or has provided a signed written informed consent, as approved by the IRB/EC (Note: This inclusion criterion is not applicable for sites where the governing IRB/EC or applicable regulation has granted a waiver of patient consent)

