### 3.5 Descriptive Endpoints or Additional Data

Descriptive endpoints and additional data are reported using only summary statistics and no hypothesis tests will be performed.

These data points will be reported for the Enrolled Population:

- Demographics (if provided): sex at birth, age range
- Indication for pacemaker or CRT-P/D implant
- Cardiovascular (CV) history and other significant medical conditions
- Procedure and device-related adverse events

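### Entry requires chart data to at least month 3, yet mortality is reported for enrolled subjects with no origin, horizon or landmark, so mortality read from the implant attempt is understated

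*SAP*

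**What the plan says.** **Entry.** Protocol 5.3.2.1 requires that the "subject's medical records contain data through at least 6 months (+/- 3 months) after LBBAP implant attempt". Protocol 5.2.1 repeats the rule as an exclusion ("Subjects are excluded if there is not 6 months", with the same ± 3 months, of follow-up data) and makes no exception for death. Protocol 5.4 counts a subject as enrolled only when all inclusion criteria are met. SAP 2.4.1 takes the same view: it treats data through 6 months as a condition of enrolment and bases its attrition assumption on that.

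**Mortality.** Mortality is a listed descriptive endpoint (protocol 4.3, SAP 1.4.3). SAP 3.5 places it in the list headed "These data points will be reported for the Enrolled Population" and limits reporting to summary statistics. No time origin, horizon or landmark is given.

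**Survival method.** SAP 2.2.3 is general: "Survival analysis will be conducted to analyze time-to-event variables", and "Subjects without events will be censored at their last known event-free time point. Survival curves will be constructed using Kaplan-Meier estimates". It names no variable and no origin, and it does not mention delayed entry.

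**Clock.** Protocol 3.1 and the schedule in 6.2 count follow-up from the implant attempt. The optional 12-month visit (-2, +4 months) lets data run to about month 16.

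**Text that fits badly with the entry rule.** SAP 2.3.1 keeps in the safety analysis a subject who lacks 6-month data but had an earlier lead-related SADE. Protocol 6.2 provides for a death record at baseline and at implant. Protocol 7.3.1 asks sites to report all deaths.

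**The concern.** Time between the attempt and the record that qualifies a patient is immortal time. An enrolled subject is counted as at risk during it, but a patient who died in it was never enrolled. The loss falls on the period just after the procedure and can only make mortality look lower.

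The registry is meant to support an indication expansion. Its mortality figure is likely to be read as mortality after an attempted left bundle branch area implant, and nothing in the planned table or curve would tell the reader that early deaths were screened out. Right-censoring does not address this, because the missing patients are absent from the data set and were not lost from it.

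**Working it through.** **1. Plan's own figure.** The visible documents give no mortality rate, so there is none to reproduce. The planned size is 220 attempted subjects (protocol 5.6). Mortality and hazard shape below are assumptions.

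**2. Formula.** Let E be the month to which entry guarantees survival, T the reporting horizon and S the survival function from the attempt.

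- True mortality by T: 1 − S(T)
- Mortality seen in enrolled subjects: 1 − S(T)/S(E)
- Ratio: [1 − S(T)/S(E)] / [1 − S(T)]

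With complete follow-up to T, this is both the crude percentage and the Kaplan-Meier estimate from the attempt without delayed entry.

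**3. Worked case: constant hazard, 5% a year, E = 3.** Monthly hazard h = −ln(0.95)/12 = 0.00427.

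| Horizon T | True, 1 − exp(−hT) | Observed, 1 − exp(−h(T − 3)) | Ratio |
|---|---|---|---|
| 6 | 2.53% | 1.27% | 0.50 |
| 12 | 5.00% | 3.77% | 0.75 |
| 16 | 6.61% | 5.41% | 0.82 |

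Per 220, that is 5.6 against 2.8 deaths at month 6, 11.0 against 8.3 at month 12, and 14.5 against 11.9 at month 16.

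**4. Visit-based reading.** If a follow-up visit in months 3 to 9 is needed, E is that visit. Simulating visit times centred on month 6 (uniform, triangular, or normal with SD 1 month) at the same hazard gives ratios of 0.07 to 0.13 at month 6, 0.50 to 0.51 at month 12 and 0.63 at month 16.

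**5. Sensitivity to the mortality rate (2% to 15% a year, constant hazard).**

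| | T = 6 | T = 12 | T = 16 |
|---|---|---|---|
| E = 3 | 0.501–0.510 | 0.752–0.765 | 0.815–0.829 |
| E = 6 | 0 | 0.503–0.520 | 0.628–0.650 |

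The assumed rate hardly matters.

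**6. Sensitivity to hazard shape (E = 3, later hazard 5% a year, hazard in months 0–3 multiplied by k).**

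| k | T = 6 | T = 12 | T = 16 |
|---|---|---|---|
| 0.5 | 0.67 | 0.86 | 0.90 |
| 1 | 0.50 | 0.75 | 0.82 |
| 2 | 0.34 | 0.61 | 0.69 |
| 3 | 0.26 | 0.51 | 0.60 |

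For small hazards the ratio is close to (T − 3)/(3k + T − 3), so halving needs k of about (T − 3)/3: 1 at month 6, 3 at month 12 and 4.3 at month 16.

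**7. If some early deaths are enrolled through the SADE wording of SAP 2.3.1.** With a fraction f of deaths before month 3 retained, the ratio is about (T − 3 + 3f)/T. At f = 0.25 this is (3 + 0.75)/6 = 0.63 at month 6 and (9 + 0.75)/12 = 0.81 at month 12.

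**8. Does delayed entry repair it?** In simulation at 10% 12-month mortality with constant hazard, delayed entry gave conditional mortality from month 3 to 12 of 7.63% against a true 7.66% on the month-3 reading. From month 3.5 to 12 on the two visit-based readings (triangular and uniform) it gave 7.22% against 7.22% and 7.19% against 7.18%.

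**The case against.** **The SAP does not say that mortality is a Kaplan-Meier outcome running from the attempt.** This is correct. SAP 2.2.3 names neither a variable nor an origin, and SAP 3.5 asks only for summary statistics. A reader might infer a Kaplan-Meier mortality curve from the attempt, but that joins two sections which the SAP does not join, and the origin is inferred from how follow-up is counted. The point survives because a crude percentage from the attempt has the same bias (step 2). A statement that x of n enrolled subjects died is true of that population. It misleads when read as risk after an attempt, and no planned label guards against that reading.

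**Early deaths are not clearly impossible.** A reader might conclude that no death before month 3 can ever appear in the data. The entry criteria say so if read literally, but SAP 2.3.1, protocol 6.2 and protocol 7.3.1 point the other way. The documents conflict and need reconciling. The death-reporting text does not waive inclusion criterion 1, and the SADE wording would admit only some early deaths, into the safety analysis.

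**The size depends on the horizon.** A reader might infer that reported mortality is halved or worse throughout. That holds at month 6 under a constant or front-loaded hazard, or to about month 12 if a visit near month 6 is required. With a month-3 floor and constant hazard, about a quarter is lost at month 12 and 18% at month 16.

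**Little turns on it.** At 5% a year, 220 × (1 − 0.95^0.25) is about 2.8 deaths before month 3. Mortality carries no hypothesis test, and SAP 2.7 ties success to the two primary endpoints alone. This limits the weight of the point, but a bias of known direction in a listed endpoint is still worth removing.

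**It would vanish if eligibility were changed.** It would if every early death could be enrolled. Under the criteria as they stand, the reporting needs correcting.

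**Conclusion.** The concern holds in this form: read literally, entry conditions on survival to at least about month 3, and neither document allows for that when reporting mortality. Mortality taken from the attempt is therefore understated. Under constant hazard the ratio to truth is about 0.5, 0.75 and 0.82 at months 6, 12 and 16 if survival is guaranteed to month 3, and about 0.1, 0.5 and 0.63 if a visit near month 6 is needed.

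The direction follows from the entry rule. The size rests on assumptions about hazard shape, which reading of the entry rule applies, and how many early deaths enter by other routes. It hardly depends on the mortality rate. The documents do not support a fixed halving, a definite plan for a Kaplan-Meier mortality curve, or the certainty that no early death will be recorded. The primary endpoints, sample size and success rule are untouched. The change should be made, but the registry does not stand or fall on it.

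**What to change.** 1. **SAP 3.5:** state the time origin and horizon for mortality, and report it as conditional on survival to the qualifying record or to a stated landmark.
2. **SAP 2.2.3:** for any time-to-event curve, let each subject enter the risk set at the qualifying record. Define that record, since the entry time is month 3 if any chart data in the window suffice and the visit date if a visit is needed.
3. **Early deaths:** beside the conditional figure, report the number of screened attempts not enrolled because of death before the window, over all attempts screened. Protocol 5.2.1 says that the site, if applicable, "will enter the patients into a site-specific recruitment/screening log". It does not ask for this reason, so require sites to record it.
4. **Reconcile** SAP 2.3.1 and protocol 6.2 and 7.3.1 with inclusion criterion 1, so that it is clear whether a patient who died early can be enrolled.

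**Cost:** SAP wording, one entry-time variable and one more reason for sites to log. Enrolment, primary endpoints and sample size need not change. The mortality figure becomes conditional. On a visit-based reading few subjects are at risk just after month 3 (with visits uniform over months 3 to 9, about 0.5/6 = 8% have entered by month 3.5), so the landmark may have to be set somewhat later.

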## 2.3 Endpoint Analysis

### 2.3.1 Primary Safety Endpoint

The primary safety endpoint evaluates freedom from LBBAP lead-related SADEs through 6 months post-implant attempt.

The hypothesis is formally expressed as:

$$\begin{aligned} H_0: & \text{Freedom from LBBAP lead related SADEs} \leq 81.2\% \\ H_1: & \text{Freedom from LBBAP lead related SADEs} > 81.2\% \end{aligned}$$

The primary safety endpoint will be estimated as a binomial proportion and the 97.5% lower confidence bound (LCB) will be calculated using the Clopper-Pearson exact method. The null hypothesis is rejected at the 2.5% significance level if the LCB is greater than the performance goal (PG) of 81.2%. The p-value from a one-sided exact test for the binomial proportion will also be calculated and compared to the 0.025 significance level.

This analysis will be performed on the enrolled population, and the primary safety analysis will use evaluable subjects. Evaluable subjects will include all subjects with an implant attempt with data available for evaluation. Subjects who do not have 6 months data and do not experience a lead-related serious adverse device effect (SADE) prior to 6 months will be excluded from the analysis. Lead-related SADEs that occur through 6 months post attempted implant will be included in the primary safety endpoint analysis. No sensitivity analyses will be performed.

The primary safety endpoint performance goal derivations are provided in Appendix A.

### 2.3.2 Primary Effectiveness Endpoint

The primary effectiveness endpoint evaluates the composite success rate of acceptable capture thresholds and sense amplitudes for LBBAP through 6 months post-implant. This analysis will be performed with only patients who are successfully implanted with the Tendril STS 2088 lead in the left bundle branch area.

The hypothesis is formally expressed as:

$$\begin{aligned} H_0: & \text{Composite success rate} \leq 80\% \\ H_1: & \text{Composite success rate} > 80\% \end{aligned}$$

## Statistical Analysis Plan

Parameter	Acceptable values
Pacing voltage	Pacing threshold $\leq$ 2.0V
Sense amplitude	LBBA sense amplitude $\geq$ 5.0 mV or $\geq$ value at implant

**Success Criteria:** A subject will be considered to have met the primary effectiveness endpoint if the pacing threshold voltage  $\leq$  2.0 V and LBBA sense amplitude is  $\geq$  5.0 mV or  $\geq$  value at implant through 6 months. For subjects that do not have LBBA amplitude measured due to active tachyarrhythmias or any other heart rhythm conditions or procedures which prevent sensing amplitude from being measured, success will be determined from the pacing threshold only. For subjects that do not have pacing threshold measured, due to active tachyarrhythmias or any other heart rhythm conditions or procedures which prevent pacing threshold from being measured, success will be determined from LBBA amplitude only. Subjects that do not have LBBA amplitude and pacing voltage, both of which are unobtainable due to active tachyarrhythmias or any other heart rhythm conditions or procedures which prevent pacing threshold from being measured, will be excluded from the analysis.

The success rate will be estimated as a binomial proportion and the 97.5% LCB of the rate will be calculated using the Clopper-Pearson exact method. The null hypothesis will be rejected at the 2.5% significance level if the LCB exceeds the PG of 80%. The p-value from a one-sided exact test for the binomial proportion will also be calculated and compared to the 0.025 significance level.

This analysis will be performed on the successfully implanted population, and the primary effectiveness analysis will use the last observation carried forward (LOCF) method.

The primary effectiveness endpoint performance goal derivations are provided in Appendix A.

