### 5.6 Number of Subjects

Data on a minimum of 220 attempted subjects will be included in order to have 190 evaluable subjects in the registry.

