## Clinical Investigation Plan

This analysis will be performed on the successfully implanted population, and the primary effectiveness analysis will use last observation carried forward (LOCF) method. Sensitivity analysis will be performed using multiple imputation.

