#### 8.3.2 Primary Effectiveness Endpoint

[REDACTED] The minimum sample size to reject the null hypothesis is 190 evaluable subjects with 85% power at 2.5% one-sided significance level.

[REDACTED]

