### 8.6 Procedures for Accounting for Missing Data

The primary safety endpoint analysis will include evaluable subjects only. The primary effectiveness endpoint analysis will use LOCF method to impute missing 6-month data and sensitivity analyses will be performed using multiple imputation. All other outcome measures will be based on the available data, with no imputation for missing values.

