### 2.4.2 Primary Effectiveness Endpoint

The assumed success rate is based on the LBBAP data in the literature. Given the lack of individual patient-level data for electrical performance, the overall implant success rate is used as a proxy to evaluate the composite success rate of acceptable capture thresholds and sense amplitudes for LBBAP through 6 months post-implant. According to the meta-analysis of 10 LBBAP studies, the overall range of LBBAP implant success rate with consideration of LBBAP electrical performance was [REDACTED] with [REDACTED] of success rate from meta-analysis.

Assuming:

- A composite success rate of [REDACTED]
- [REDACTED] power
- Binomial exact test
- One-sided alpha of 0.025
- Performance goal of 80%

The minimum sample size to reject the null hypothesis is [REDACTED] evaluable patients. Assuming approximately [REDACTED] of subjects will not have a successful LBBAP implant per protocol, and that about [REDACTED] of subjects will not have evaluable capture threshold and/or sense amplitudes, [REDACTED] subjects will be enrolled to ensure that [REDACTED] subjects are evaluable for the primary effectiveness endpoint. Evaluable subjects are defined in Section 2.3.2.

The sample size calculation was performed using the PASS 15 Tests for One Proportion module.

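### The primary effectiveness analysis drops subjects whose two lead readings are both unobtainable, without ranking that exclusion against LOCF or saying how a revised or removed lead counts

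*SAP*

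**What the plan says.** The Success Criteria in SAP 2.3.2 and CIP 8.2.2 handle unobtainable readings in two ways. If a rhythm condition or a procedure prevents one of the two readings, the other reading alone decides success. If both are prevented, the subject leaves the analysis. The SAP sentence ends: "any other heart rhythm conditions or procedures which prevent pacing threshold from being measured, will be excluded from the analysis". The CIP sentence ends the same way. Neither document defines *procedures*.

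The analysis set and the missing-data rule are stated separately. CIP 8.2.2: "This analysis will be performed on the successfully implanted population, and the primary effectiveness analysis will use last observation carried forward (LOCF) method". SAP 2.3.2 says the same. CIP 8.6 adds, with no exception: "The primary effectiveness endpoint analysis will use LOCF method to impute missing 6-month data". The CIP criterion applies at 6 months; the SAP criterion applies through 6 months.

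SAP 2.4.2 expects some loss. It allows for failed implants and for a share (redacted) "of subjects will not have evaluable capture threshold and/or sense amplitudes", and refers to SAP 2.3.2 for the definition of evaluable. CIP 5.6: "Data on a minimum of 220 attempted subjects will be included in order to have 190 evaluable subjects in the registry".

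The only sensitivity analysis in the readable text is multiple imputation on the successfully implanted population (SAP 2.3.2.1 and 2.12). Its model in Appendix B and part of SAP 2.9 are redacted.

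**The concern.** Take an implanted subject with a failing threshold at an unscheduled visit and no obtainable readings at 6 months because of a rhythm condition. Under LOCF this subject is a failure. Under the Success Criteria the subject is absent from numerator and denominator. Both are fair readings of the plan, and they can give different primary results.

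The second gap is the lead that is no longer there. Revision or explant (CIP 6.1.3), system revision and product out of service (CIP 6.2) are all collected, but no readable text says how such a subject scores for effectiveness. A removed lead cannot be tested, so the unlimited word *procedures* can be read to cover it, and the loss of the lead may itself reflect its performance. The safety endpoint is more careful: under SAP 2.3.1, a subject without 6-month data who had a lead-related SADE stays in. Known effectiveness failures have no matching protection.

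The endpoint is one proportion tested against a fixed 80% goal. There is no control arm in which the same exclusion could balance out, so every failure removed raises the estimate and its lower bound directly.

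**Working it through.** **Inputs**
- Test: Clopper-Pearson one-sided 97.5% lower confidence bound (LCB) must exceed 80% (SAP 2.3.2).
- Size: 190 evaluable, 85% power, one-sided 2.5% (CIP 8.3.2).
- 220 attempted to give 190 evaluable (CIP 5.6), an allowance of 30 that also covers failed implants; the split is redacted.
- Assumed success rate: redacted in SAP 2.4.2. Back-solved below, so an assumption.
- Number excluded (m) and their true success rate (q): not given. Ranges are shown.

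**Step 1. The plan's own figure.** The smallest r with P(X ≥ r | n = 190, p = 0.80) ≤ 0.025 is r = 163, with tail probability 0.02497. At an assumed rate of 88.0%, P(X ≥ 163 | 190, 0.88) = 85.3%, and 190 is the first n to reach 85%. Rates from 87.98% to 88.25% give an n within 3% of 190. The stated n is consistent with about 88%, but this is back-solving, not an independent check.

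**Step 2. How few subjects matter.** LCB = the 0.025 quantile of Beta(x, n − x + 1).

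| Result | Rate | LCB | Goal met |
|---|---|---|---|
| 162/190 | 85.3% | 79.4% | no |
| 163/190 | 85.8% | 80.002% | yes |
| 163/191 (one excluded failure restored) | 85.3% | 79.5% | no |
| 164/191 (one excluded success restored) | 85.9% | 80.1% | yes |
| 167/190 | 87.9% | 82.4% | yes |
| 167/195 (five excluded failures restored) | 85.6% | 79.9% | no |

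**Step 3. Direction and size.** With 190 analysed at 88% and m excluded at rate q, the rate in all 190 + m is (190 × 0.88 + m × q)/(190 + m). The bias from exclusion is therefore m/(190 + m) × (0.88 − q).
- m = 2, q = 0: 2/192 × 0.88 = +0.92 points.
- m = 4, q = 0: 4/194 × 0.88 = +1.81 points.
- m = 4, q = 0.50: 4/194 × 0.38 = +0.78 points.
- m = 2, q = 0.60: 2/192 × 0.28 = +0.29 points.
- q = 0.88: zero for any m. Above 0.88 the bias is negative.

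**Step 4. Error rate if the true rate in all implanted subjects is 80%.** Holding 190 analysed, the rate among them is p = [0.80 × (190 + m) − m × q]/190, and the error is P(X ≥ 163 | 190, p).
- m = 2, q = 0: p = 153.6/190 = 0.8084, error 4.7%.
- m = 4, q = 0: p = 155.2/190 = 0.8168, error 8.2%.
- m = 4, q = 0.50: p = 153.2/190 = 0.8063, error 4.0%.
- m = 2, q = 0.60: p = 152.4/190 = 0.8021, error 2.9%.

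Holding 190 implanted instead, so that 190 − m are analysed, the q = 0 errors are 3.5% (2 excluded) and 7.4% (4 excluded). If the excluded are all successes, the error with 2 excluded falls to 1.5%.

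**Step 5. Exclusion against LOCF.** The readable text does not bar carrying the implant reading forward. A carried implant amplitude equals the implant value, so it meets the sensing criterion by construction, and success then needs only a carried threshold of 2.0 V or less. With 190 implanted and 4 affected:
- excluded: 160/186 = 86.0% (LCB 80.2%, met);
- LOCF, all four carried as successes: 164/190 = 86.3% (LCB 80.6%, met);
- counted as failures: 160/190 = 84.2% (LCB 78.2%, not met).

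**The case against.** The clause is about whether a reading can be taken, not about whether the lead failed. A poor threshold that is measured still counts as a failure, and a tachyarrhythmia on the day of the visit may have nothing to do with the lead. The exclusion is prespecified and the sample size anticipates it. A revision that amounts to a lead-related SADE counts against the co-primary safety endpoint, and both endpoints must be met (SAP 2.7). The text also allows LOCF to be applied first, so that only subjects with no usable reading are excluded; on that reading, earlier failing values are kept.

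Most of this stands, and it limits the point. A reader might infer that the exclusion raises the success rate. The documents do not show that: Step 3 gives zero bias when the excluded succeed as often as the rest, and Step 5 shows that LOCF from the implant visit could give a higher rate than exclusion. A reader might also infer that the exclusion overrides LOCF. Precedence is simply not stated, and part of SAP 2.9 is redacted.

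Two things are not answered. The safety endpoint does not catch a revision that was not a serious lead-related event. And a benign reading of *procedures* or of the order of rules, however sensible, is not written down.

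**Conclusion.** The point holds as a conflict between two rules, with an undefined term, in the primary effectiveness analysis. The plan permits an analysis that leaves out subjects with earlier failing readings and subjects who lost the lead, and the readable text supplies no count or failure-counted analysis that would reveal it. If those subjects fail more often than the rest, the rate is inflated against the 80% goal; whether they do, and by how much, cannot be determined from the documents.

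The 4.7% and 8.2% error rates are worst-case figures: every excluded subject a failure, 190 analysed, true rate 80%. The 163/190 example sits exactly at the cut-off and flips only if the restored subject is a failure. The bias figures rest on the back-solved 88%. None of these is an expected effect. The change is a cheap improvement, worth making before analysis because the result can turn on one subject.

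**What to change.** In SAP 2.3.2 and CIP 8.2.2:

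1. Apply LOCF, from readings obtained after the implant procedure, before any exclusion. Only subjects with no usable post-implant reading can then be excluded.
2. State that *procedures* does not include revision, replacement, removal or taking out of service of the LBBA lead, and that these subjects stay in the denominator as not successful.
3. Report the number excluded by reason, and add a sensitivity analysis that counts every excluded subject as a failure.

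Subjects who are unreadable for rhythm reasons alone, with no post-implant reading, can stay excluded from the primary analysis. Scoring them as failures there is debatable and could bias the rate downward; item 3 shows the effect without imposing it.

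The cost is a wording change in two places and one extra table. The data are already collected: unscheduled visits, system revision and product out of service (CIP 6.2), and revision or explant (CIP 6.1.3). The downside is that the reported rate may be slightly lower, and a lead taken out of service for a reason unrelated to its performance would count against it.
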